### *Outcomes*

#### PRIMARY OUTCOMES

TITLE: Survival rate of 4 mm implants

DESCRIPTION:

-To compare the survival rate of 4 mm implants used as distal support of a maxillary full-arch FDPs with standard (10 mm) implants placed in association with a bilateral sinus floor augmentation procedure.

TIME FRAME: 24 months

TITLE: Changes of crestal bone level

DESCRIPTION: Change of crestal bone level measured on intraoral x-ray applying a parallel technique from baseline (definitive prosthesis delivering) and 2-year follow-up. The distance between the implant margin and the first bone to implant contact will be measured in millimeters at the mesial and distal aspects of the Short and Standard implants.

TIME FRAME: 24 months

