## **Abstract**

**Aim:** to compare the survival and success rates of 4 mm implants used as distal support of a maxillary full-arch FDPs with standard (10 mm) implants placed in association with a bilateral sinus floor augmentation procedure.

**Material and Methods:** Two groups will be randomly prepared, the Short group and the Standard group. In the Short group, one 4 mm long and 4.1 mm in diameter implant (extra-short implant) will be installed in each side of the posterior region of the maxilla. In the Standard group, bilateral sinus floor elevations will be performed. After 4 months of healing, one 10 mm long and 4.1 mm in diameter implant (standard implant) will be installed into each augmented sinus. In the frontal region, four 10 mm long implants will be installed in both groups. Clinical assessments and x-rays will be taken at prosthesis delivering (6-8 weeks after implant installation), and after 6, 12, 18 and 24 months.

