## Introduction

Anatomical limitations to implant insertion in fully edentulous arches are frequently encountered in the posterior regions of the jaws, due to the presence of the mandibular canal and of the maxillary sinus. In such situations, the installation of standard implants ( $\geq 10$  mm) could be impossible.

An alternative might be the use of the so-called “tilted implants” that might allow the use of standard implants. Vertical augmentation procedures or sinus floor elevation might allow the installation of standard implants as well. Another alternative is the use of short implants, as recommended in a consensus conference for the lower occurrence of complications of this treatment compared the use of longer dental implants installed in augmented sinus. Another consensus report concluded that the use of  $\leq 6$  mm long implants are a valid option to be used as alternative to augmentation procedures to reduce morbidity incidence.

A recent article reported a high survival rate (91.7%) after 10 years of loading of 6 mm long implants supporting single FDPs in the posterior regions of both jaws. Recently, 4 mm long implants with a standard diameter have been used for the restoration of the posterior edentulous mandible with favorable results. However, RCTs reporting the results from full-arch FDPs that included 4 mm long implants placed in the posterior regions of the maxilla have not been published yet.

Hence, the aim of the present study will be to compare the survival and success rates of 4 mm implants used as distal support of a maxillary full-arch FDPs with standard (10 mm) implants placed in association with a bilateral sinus floor augmentation procedure.

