### *Study population*

This study will be designed as an RCT study. Twenty patients have been planned to be included in the present RCT. Two parallel groups will be randomly arranged, the Short group that will include the 4 mm long implants, and Standard group that will include only 10 mm long implants installed 4 months after bilateral sinus floor elevation. Participants recruitment and all clinical procedures will be performed at the Department of Biomedical and Neuromotor Sciences, Dental Clinic, University of Bologna, RN, Italy.

The following inclusion criteria will be adopted:

- Edentulous maxilla
- Willing to receive a full arch fixed restoration in the maxilla.
- Latest extraction at least 8 weeks before implant insertion
- Sinus floor height included between 4 to 6 mm
- Bone width in the distal segments sufficient to allow the insertion of a 4 mm long implant of standard diameter.
- In the anterior maxilla (from first premolar to first premolar) bone width sufficient to allow the insertion of 10 mm long implants of standard diameter.

Minor horizontal augmentations with GBR procedures was allowed in the anterior maxilla.

Moreover, the opposing arch have to present one of the following conditions:

- natural dentition (at least 10 elements from 3.5 to 4.5)
- FPDs of at least 10 elements (from 3.5 to 4.5) supported by teeth or implants
- Implant supported or teeth supported overdentures
- Adequate partial removable prostheses.

*Exclusion criteria:*

Systemic exclusion criteria

- Presence of conditions requiring prophylactic use of antibiotics (e.g., history of rheumatic heart disease, bacterial endocarditis, cardiac valvular anomalies, prosthetic joint replacements).

- Major systemic diseases, or medical conditions requiring prolonged use of steroids, or alcoholism or chronically drug abuse.
- Current pregnancy or breastfeeding women
- Smokers > 10 cigarettes per day
- Physical handicaps that would interfere with the ability to perform adequate oral hygiene
- Immunocompromised patients including patients infected with HIV
- Conditions or circumstances, in the opinion of the investigator, which would prevent completion of study participation or interfere with analysis of study results, such as history of non-compliance, or unreliability.
- Patients with an ongoing or previous treatment with bisphosphonates (for at least 2 months for oral therapy or 6 months for IV injection)

*Local exclusion criteria*

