- Local inflammation, including untreated periodontitis
- Pre-cancerous oral lesions
- History of local irradiation therapy
- Severe bruxism or clenching habits
- Patients with inadequate oral hygiene or unmotivated for adequate oral home care
- Previous GBR or GTR treatment at the implant site
- Total removable prosthesis in the lower arch

*Randomization and assignment concealment*

A statistician not involved in the study performed the randomization in blocks of four and the assignments will be sealed in coded and opaque envelopes.

*Masking Procedure:* The surgeon will be blinded about the assignment until the time of the surgery. The outcome assessor will be blinded about the protocol.

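### Could an implant lost between installation and prosthesis delivery escape both primary outcomes?

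*Combined protocol and SAP*

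**What the plan says.** Two primary outcomes are listed in the Primary Outcomes section. The first is to "compare the survival rate of 4 mm implants used as distal support of a maxillary full-arch FDPs with standard (10 mm) implants placed" with sinus augmentation. The second is "Change of crestal bone level measured on intraoral x-ray applying a parallel technique from baseline (definitive prosthesis delivering) and 2-year follow-up". Each carries only "TIME FRAME: 24 months".

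The bone-level outcome has a clear origin, prosthesis delivery, which Radiographic measurements also labels as baseline. Survival has none. The plan does not define failure or a denominator. Data analysis names only bone-level change as the primary variable and gives a test for that alone.

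On timing, the Abstract says: "Clinical assessments and x-rays will be taken at prosthesis delivering (6-8 weeks after implant installation), and after 6, 12, 18 and 24 months". Prosthetic procedures puts impressions at six weeks, with delivery within a further week. The Standard group is described as the "Standard group that will include only 10 mm long implants installed 4 months after bilateral sinus floor elevation".

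On size: "Twenty patients have been planned to be included in the present RCT", and "A statistician not involved in the study performed the randomization in blocks of four". Each patient receives one posterior implant per side.

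**The concern.** An implant that fails before delivery has no delivery film, so it has no bone-level change to analyse. Only survival can then record the loss, and the text does not say when survival starts. Several features could suggest a count from delivery:

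- Delivery is the only time called baseline.
- Probing and plaque assessments begin there.
- The Introduction cites a rate expressed by time in loading: "A recent article reported a high survival rate (91.7%) after 10 years of loading of 6 mm long implants supporting single FDPs".
- The 4 mm implants are described by their role in supporting the prosthesis, which an implant lost before delivery never fills.

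On that reading an early loss appears in no named outcome, because the only secondary outcome covers technical complications. The starting point could also be chosen after the losses are known. With few implants per group, the reported rate would move visibly. The time from first surgery to delivery also differs between groups, which suggests that the exclusions might be unbalanced.

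**Working it through.** The plan states no power, event rate or margin, so there is no figure of its own to reproduce. The check has three parts.

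**1. How much the starting point can matter**

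Inputs: 20 patients (Study population); blocks of four (Randomization and assignment concealment); two posterior implants per patient (both surgical sections). The allocation ratio is not stated, so equal allocation is assumed. Then 20/4 = 5 full blocks, 10 patients per group, and 10 × 2 = 20 posterior implants per group.

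With *e* losses before delivery and *l* after it, survival is (20 − e − l)/20 from installation and (20 − e − l)/(20 − e) from delivery.

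| e | l | From installation | From delivery | Difference (points) |
|---|---|---|---|---|
| 0 | 1 | 19/20 = 95.0% | 19/20 = 95.0% | 0 |
| 1 | 0 | 19/20 = 95.0% | 19/19 = 100% | 5.0 |
| 1 | 1 | 18/20 = 90.0% | 18/19 = 94.7% | 4.7 |
| 2 | 0 | 18/20 = 90.0% | 18/18 = 100% | 10.0 |

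Exact (Clopper-Pearson) 95% intervals for a single early loss are 75.1-99.9% from installation and 82.4-100% from delivery. They overlap almost entirely.

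For *k* losses against 0 in 20 v 20 implants, the two-sided Fisher p is 2 × C(20,k)/C(40,k):

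- k = 4: 2 × 4,845/91,390 = 0.106
- k = 5: 2 × 15,504/658,008 = 0.047

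So five early losses in one group and none in the other would be needed for significance. The intervals and the test treat implants as independent and ignore pairing within a patient.

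The documents give no early-loss rate. If the rate per implant were 1%, 2%, 5% or 10%, the chance of at least one early loss in a group, 1 − (1 − p)^20, would be 18%, 33%, 64% or 88%.

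**2. Whether the text points to a count from delivery**

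- Clinical evaluation also records bone quality and insertion torque, which belong to installation. Radiographic measurements schedules a film at installation. The implants are therefore observed from placement.
- The baseline label belongs to the radiographic outcome. Nothing attaches it to survival.
- The rate cited in the Introduction gives a length of follow-up. The documents do not say whether that study left out losses before loading. It also concerns 6 mm implants under single restorations in both jaws.
- The wording about distal support repeats the aim and says what the implants are for. Reading it as a denominator for one group, and *placed* as a different denominator for the other, is strained.

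**3. Whether the window differs between groups**

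| Interval | Short | Standard |
|---|---|---|
| First surgery to installation | none | 4 months (about 17.4 weeks) |
| Installation to delivery | 6-8 weeks | 6-8 weeks |
| First surgery to delivery | 6-8 weeks | 17.4 + 6 = 23.4 to 17.4 + 8 = 25.4 weeks |

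The ratios 23.4/6 = 3.9 and 25.4/8 = 3.2 come entirely from graft healing, when no posterior Standard implant exists and none can be lost. The window in which a placed implant can fail before delivery is equal. The longer wait bears on patients who never reach implant placement, which is a separate attrition question.

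**The case for a change.** The strongest case for a change is that survival is a named primary outcome and comparing survival is the stated aim. The plan nevertheless leaves its start, failure definition, denominator and analysis unwritten. At 20 implants per group, one early loss separates a report of 95% from one of 100%, and nothing in the text stops that choice being made after the data are seen. Writing the definition down would take a few sentences and no extra visit or film.

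The facts in this argument stand: the definition is absent, the arithmetic is right, and a loss before delivery cannot enter the bone-level outcome. It does not follow that the loss goes uncounted. An unstated start leaves the matter open, and the usual way of closing it is to count all implants placed, which makes the early loss a failure. The argument shows that an analyst could choose badly. It does not show that the plan tells them to.

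**Conclusion.** No change to the plan is needed. The survival outcome lacks a written origin, failure definition and denominator. This is missing detail that an analyst would ordinarily supply by counting every posterior implant placed, from installation, in the same way in both groups. On that count an early loss is recorded as a failure. The delivery baseline for bone level is legitimate and unaffected.

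If survival were instead counted from delivery, each early loss would raise that group's reported rate by up to 5 percentage points. No formal comparison would turn on this short of 5 losses against 0. This sizing assumes equal allocation (20 posterior implants per group) and independence of implants within a patient. How many early losses to expect cannot be taken from the documents. A reader of the results should check that the survival denominators match the number of implants placed.

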#### SECONDARY OUTCOMES

TITLE: Technical complications

DESCRIPTION:

Technical complications: any technical complications related to implants, abutments, screw loosening, prosthetic fracture or chipping of the veneer material expressed in number of occurrence.

TIME FRAME: 24 months

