#### *Prosthetic procedures*

During the healing, a temporary removable prosthesis will be provided to the patients.

Six weeks after implant installation, impressions will be taken and a fixed metal ceramic full-arch screw-retained prosthesis will be fabricated and delivered within a week.

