### *Data analysis*

Mean values will be obtained from the double measurements made at the mesial and distal aspects of each implant. Mean values will be calculated between the distal and mesial measurements for each implant.

At the tissue level implants, the height of the polished neck (1.8 mm) will be subtracted to obtain the level of the coronal margin of the rough surface. The marginal bone levels reported in the present article will be related to the position of the coronal marginal rough surface. Marginal bone changes over time will be calculated and differences between groups will be evaluated at implant level using

the Mann-Whitney test included in the Statistics software SPSS (IBM Inc., Chicago, IL, USA) The level of significance will be set at  $\alpha=0.05$ .

The primary variable will be the change of marginal bone level between the baseline and 1 and 2 years of follow-up.

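### Technical complications, the only listed secondary outcome, are a bare event count: it hides how many patients are affected and depends on time in function

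*Combined protocol and SAP*

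**What the plan says.** The combined protocol and SAP lists one secondary outcome, technical complications. The section Secondary outcomes covers any such complication of implants or abutments, and then "screw loosening, prosthetic fracture or chipping of the veneer material expressed in number of occurrence". The window is "TIME FRAME: 24 months". The outcome is not defined per patient, per prosthesis or per unit of time.

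Under Prosthetic procedures, "a fixed metal ceramic full-arch screw-retained prosthesis will be fabricated and delivered within a week", so each patient contributes one prosthesis. Under Study population, "Twenty patients have been planned to be included in the present RCT" and "Two parallel groups will be randomly arranged". Under Randomization and assignment concealment, a statistician "performed the randomization in blocks of four". The Abstract gives the visits: "Clinical assessments and x-rays will be taken at prosthesis delivering (6-8 weeks after implant installation), and after 6, 12, 18 and 24 months".

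Data analysis describes one between-group test, a Mann-Whitney test on marginal bone change. It says nothing about technical complications. No section says how to count a patient who withdraws or a prosthesis that goes out of use, and no dropout rate is given.

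**The concern.** A raw number of events mixes three things: how many patients had a problem, how often it recurred in the same patient, and how long the prostheses were in use. With about 10 prostheses per arm, a single patient with repeated screw loosening or chipping can dominate the total. Repeat events in one mouth are not independent evidence about the treatment.

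These events can occur only while the prosthesis is in function. A patient who leaves, or whose prosthesis is taken out of use, stops adding events. If this happens more in one arm, that arm's total understates its complications. A reader of the report could not tell whether a low total means few complications or little exposure, or whether a high total means one problem prosthesis or many.

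**Working it through.** The documents give no complication rate, dropout rate or power figure, so there is no stated result to reproduce. What follows shows how the metric behaves under labelled assumptions.

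**Inputs from the documents:** 20 patients (Study population), blocks of four (Randomization and assignment concealment), one prosthesis per patient (Prosthetic procedures), 24 months (Secondary outcomes).

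**Assumptions:** 1:1 allocation, which is not stated; the 24 months run from prosthesis delivery, as the visits do; losses occur in one arm only and are unrelated to complication risk.

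**1. Arm size.** 20 / 4 = 5 complete blocks, each with 2 patients per arm, so 10 prostheses per arm.

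**2. Clustering.** Five events may all be in one patient (1/10 = 10% affected) or in five patients (5/10 = 50% affected). The reported total is 5 in both cases. This needs no dropout.

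**3. Exposure.** Full exposure per arm is 10 × 24 = 240 patient-months, or 20 patient-years.

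- Two patients stop at 6 months: 8 × 24 + 2 × 6 = 204 months (17 patient-years). 204/240 = 0.85, a fall of 15%.
- Three stop at 6 months: 7 × 24 + 3 × 6 = 186 months (15.5 patient-years). 186/240 = 0.775, a fall of 22.5%.

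**4. When the order reverses.** Expected events = rate × exposure. Suppose the arm with the losses has the higher true rate, and let the rate ratio be that arm's rate over the other's. Its expected count falls below the other arm's when the rate ratio is below 20 / (its exposure).

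The last three columns assume 0.2 events per patient-year in the better arm (0.2 × 20 = 4.0 expected events) and a true rate ratio of 1.5. The probabilities treat the two totals as independent Poisson counts.

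| Patients in the worse arm stopping at 6 months | Its exposure (patient-years) | Expected counts reverse if rate ratio is below | Expected events, worse v better | Ratio of expected counts | Probability that the worse arm shows fewer events |
|---|---|---|---|---|---|
| 0 | 20 | 1.00 | 6.0 v 4.0 | 1.50 | 0.21 |
| 2 | 17 | 1.18 | 5.1 v 4.0 | 1.28 | 0.30 |
| 3 | 15.5 | 1.29 | 4.65 v 4.0 | 1.16 | 0.35 |
| 4 | 14 | 1.43 | 4.2 v 4.0 | 1.05 | 0.40 |
| 5 | 12.5 | 1.60 | 3.75 v 4.0 | 0.94 | 0.46 |

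**5. Range.** With better-arm rates of 0.1 to 0.4 per patient-year and rate ratios of 1.25 to 2.0, the probability in the last column is 0.04 to 0.32 with full follow-up, 0.09 to 0.40 with two losses and 0.14 to 0.47 with three.

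**6. The rate.** Dividing expected events by exposure gives 0.30 v 0.20 per patient-year in every row, for example 5.1/17 = 0.30 and 4.0/20 = 0.20. The ratio stays at 1.5 provided loss is unrelated to complication risk.

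**The case against.** The strongest reply is that the plan does not say the counts will be tested, or even pooled into one total per arm. A descriptive listing by type and patient, feasible with 20 patients, would remove most of the problem. The first part stands: a between-group comparison is inferred from the two-arm design. The second part is only a possibility, because the metric that the plan states is the number of occurrences.

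A reader might go further and infer that the worse arm will look better, or that the outcome rewards early failure. The documents do not support that:

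- They give no dropout figure, so one-sided loss is an assumption. At a true rate ratio of 1.5, even four losses of 10 at 6 months do not reverse the expected counts; five do. Smaller losses only shrink the difference.
- With full follow-up, chance alone puts the worse arm ahead about 21% of the time in the illustration. The outcome is imprecise under any metric.
- Implant loss is captured separately, since implant survival at 24 months is a primary outcome.
- The definition opens with any technical complication, so it cannot be assumed that loss of a prosthesis would add no event.
- Each prosthesis is planned on six implants (two posterior and four frontal), and nothing says that losing one takes the prosthesis out of use.

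Nor do the documents set a rule for technical acceptability that this outcome would decide.

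The remedy has its own limits. A proportion of patients affected still counts an event-free withdrawal as a non-event. Counting removals for biological reasons as technical complications would blur the outcome. Clinical evaluation does not list technical complications among its assessments, so it cannot be taken for granted that their dates are recorded. The fix allows for each of these.

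**Conclusion.** The point holds as a minor one about a secondary outcome; the primary outcomes are unaffected. The stated metric is a poorer summary than the design allows. The clustering problem holds at any level of follow-up: with 10 prostheses per arm, one total is compatible with 10% or 50% of patients affected. The exposure problem is conditional. It needs unequal time in function, and 2 or 3 one-sided losses at 6 months would cut one arm's exposure by 15% or 22.5%. That weakens a true difference, and reverses expected counts only below a rate ratio of about 1.18 or 1.29. If all patients complete 24 months with the prosthesis in function, there is no exposure bias. These figures rest on 1:1 allocation and on assumed losses; the event probabilities also rest on assumed complication rates.

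**What to change.** In Secondary outcomes, report by randomised group:

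- (a) the number of patients with at least one technical complication out of those given a prosthesis, with the number followed to 24 months beside it, so that event-free withdrawals are visible;
- (b) events per prosthesis-year in function, with time at risk ending at the last visit or when the prosthesis goes out of use.

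Keep the total count by type as a listing. Report removal, remake or conversion of the prosthesis on a separate line with its cause, and do not merge it into technical complications. The separate line is needed because (b) corrects for exposure only and does not show why a prosthesis went out of use.

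The cost is two or three extra table rows. The date on which a prosthesis goes out of use or a patient withdraws must also be recorded, at least to the nearest visit; the scheduled visits already provide that grid.
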